## **PROTOCOL SYNOPSIS**

Protocol Title:	The Effect of Lysulin on Glycemic Control and Advanced Glycation in Inadequately Controlled Type 2 Diabetes Mellitus: A Double blinded Placebo Controlled Study
Site Numbers & Names:	Phoenix VA Health Care System
Research Hypothesis:	Dietary supplement (Lysulin™) reduces blood glucose, hemoglobin A1c and Advanced Glycation Endproducts in individuals with inadequately controlled type 2 diabetes.
Study Schema: Drugs / Doses / Length of Treatment)	Lysulin 3,330 mg/d (two 555mg tablets TID) x 12 weeks
Study Objectives: 

• Primary:

• Secondary:

	The primary objective is to determine whether 12 weeks of treatment with Lysulin, compared to placebo, causes a reduction from baseline in the plasma levels of glucose, hemoglobin A1c (HbA1c) and Advanced Glycation End products (AGEs) in patients with inadequately controlled type 2 diabetes mellitus. Secondary objectives include determining whether 12 weeks of treatment with Lysulin increases beta-cell function as measured by plasma C-peptide levels.
Study Design	This is a randomized, prospective, double-blind study. Randomization to Lysulin and placebo will be in a 1:1 fashion.
Accrual Goal: (Total number of subjects)	60 subjects for the successful completion of 56 subjects
Accrual Rate: (Number of subjects expected per month)	15 subjects/month
Correlative Studies: (PK/PD, etc.)	N/A
Inclusion Criteria:	
 
1. Signed written informed consent
 
2. Able to communicate meaningfully with the investigator and legally competent to provide informed written consent
 
3. Men and women, ages 21-75 years
 
4. Diabetes, with HbA1c <math>\geq</math> 7.5 % and <math><</math> 10% within 6 weeks of screening
 
5. Stable dose of insulin (<20% change in units) 6 weeks prior to enrollment
 

Exclusion Criteria:	
1) Sex and Reproductive Status
 
 
a) Women of child-bearing potential who are unwilling or unable to use an acceptable method to avoid pregnancy for the entire study period.
 
b) Women who are pregnant or breastfeeding
 

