
Criteria for Evaluation: Efficacy, safety, stopping rules, etc.)	Study participation will be stopped for adverse effects at the discretion of the study investigator. Subjects may stop study participation at any time and for any reason. Enrollment may be stopped due to futility or efficacy by interim analysis.
Statistical analysis:	A linear mixed effects model will be used to evaluate treatment-induced endpoints. The models will be fit for sequential values of the response variable (including the baseline measurement).
Statistical power:	54 participants will be required to complete the study to detect a of 0.7% points reduction in HbA1c and 19 mg/dl reduction in fasting plasma glucose levels with 80% power at the alpha level of 0.05. This corresponds to SDs for HbA1c 0.9% points and fasting glucose 25 mg/dl.

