Study Visits Schedule: All visits will be performed in the Clinical Research Center (CRC) at the Phoenix VA. Completion of the entire study will involve up 3-4 visits to the CRC. After initial visit for obtaining of informed consent and screening, qualified patients will undergo a baseline testing (on the same day as screening visit or on a separate day), including blood collection for baseline measurements, and will be randomized to treatment (Lysulin™ or matching placebo). Study medication will be dispensed to the subject in a double-blinded fashion by Phoenix VA research pharmacist. Subjects will be instructed to take two tablets orally with breakfast, lunch and dinner. They will return to the CRC for clinical evaluation and blood draws after 6 and 12 weeks (final visit). Subjects will be instructed to not make major lifestyle modifications, including changes to their diet or exercise, during their study participation. At least one phone call contact will take place between interim visits to ensure medication is being taken appropriately and to help address any study related questions. At each visit a comprehensive assessment of side effects, medication compliance/competency and concurrent medical history will be obtained and entered into the database. Additional brief visits may occur as needed to ensure participant comfort/competency with treatment.

Study endpoints:

Primary: Fasting plasma glucose and HbA1c concentrations

Secondary: Fasting plasma AGEs, C-peptide concentrations and lipid measurements

Recruitment Approach: Participants will be recruited utilizing VA electronic medical records to identify potential candidates meeting inclusion criteria, as well as from the Phoenix VA primary care, specialty and women's clinics, community diabetes clinics, ads in VA newsletters and flyers,

permission to be contacted forms, on hold message, social media, clinic list, BISL, list of A1c results from lab, and through VINCI.

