Statistical Analysis Plan: Univariate numerical and graphical procedures will be used to explore distributional characteristics and dependence structure of measured variables. Data transformations (e.g., logarithm) may be used to improve distributional characteristics and/or to improve linearity of relationships between response and covariates. A linear mixed effects model will be used to evaluate treatment-induced endpoints (glucose, HbA1c, AGEs, C-peptide). This approach allows the inclusion of potential covariates, and explicitly accounts for repeated measurements on each patient (and patient-to-patient variability). We will fit models to all sequential values of the response variable (including the baseline measurement), rather than computing a change score. This structure allows statistically efficient evaluation of treatment effects and allows modeling of differential treatment effects for patients with varying initial glycemic control.

Power Calculation: 54 participants will be required to complete the study to detect a 0.7% points reduction in HbA1c and 19 mg/dl reduction in fasting plasma glucose levels with 80% power at the alpha level of 0.05. This was based on SDs for HbA1c=0.9% points and fasting glucose=25 mg/dl from our previous study in patients with > 5 years duration of type 2 diabetes.

Interim analysis: Using a 2-stage group sequential trial design, an interim analysis will be performed by an independent statistician after completing first 28 participants, i.e. 14 per group. The sample size for interim analyses as well as the boundary values for the treatment effect were computed by SEQDESIGN procedure of SAS v9.4. The SEQTEST procedure will compare the test statistic with the boundary values at the interim stage so that the study can be stopped to reject or accept the null hypothesis. If the interim analysis will indicate futility, the enrollment of new patients will be discontinued. All active participants will complete the study as planned.

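### Fasting glucose and HbA1c are both primary under one alpha of 0.05 and one 80% power, with no rule for success and no endpoint tied to the interim boundary

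*Combined protocol and SAP*

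**What the plan says.** Study Approach, Study endpoints, gives two primaries: "Primary: Fasting plasma glucose and HbA 1c concentrations". The Power Calculation covers both in one sentence, a "0.7% points reduction in HbA1c and 19 mg/dl reduction in fasting plasma glucose levels with 80% power at the alpha level of 0.05", using SDs of 0.9 percentage points and 25 mg/dl. The synopsis repeats it: "54 participants will be required to complete the study to detect a of 0.7% points reduction in HbA1c", with the same glucose target, power and alpha. Sidedness is not stated.

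The Statistical Analysis Plan paragraph applies a linear mixed model to glucose, HbA1c, AGEs and C-peptide: "We will fit models to all sequential values of the response variable (including the baseline measurement), rather than computing a change score". Neither it nor any other section gives an either/both rule, a testing order or a division of alpha.

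The synopsis says "Enrollment may be stopped due to futility or efficacy by interim analysis". The Interim analysis paragraph places one look after 28 completers: "The SEQTEST procedure will compare the test statistic with the boundary values at the interim stage", so that the null can be rejected or accepted. It refers to a single statistic and a single null hypothesis and names no endpoint.

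On a smaller matter, the synopsis primary objective asks whether treatment "causes a reduction from baseline in the plasma levels of glucose, hemoglobin A1c (HbA1c) and Advanced Glycation End products (AGEs"), whereas Study endpoints has "Secondary: Fasting plasma AGEs, C-peptide concentrations and lipid measurements".

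**The concern.** With two primary endpoints, a type I error rate of 5% and a power of 80% have a meaning only once success is defined. An either-endpoint rule at full alpha gives up error control across the pair. A both-endpoints rule keeps error control and gives up power. A fixed order keeps both for the first endpoint. The plan does not choose, and a choice made after the data are unblinded would not be credible.

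The same gap reaches the interim. Two primaries give two statistics and two null hypotheses, and the independent statistician is told to compare one unnamed statistic with the boundary. If one endpoint crosses and the other does not, the plan does not say whether the null has been rejected.

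**Working it through.** **Inputs from the documents.** Effects 0.7 percentage points and 19 mg/dl; SDs 0.9 and 25; alpha 0.05; power 80%; 54 completers (Power Calculation). Allocation 1:1; 60 enrolled for 56 completers; 15 subjects per month (synopsis). Interim at 28 completers.

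**Assumed.** Two-sided testing, because it reproduces the plan's number and one-sided does not (one-sided 0.05 by the normal formula needs only 42 for HbA1c and 44 for glucose). Endpoint correlation r from 0 to 0.9, because the documents give none.

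**1. Reproducing the 54.** Two-sample t-test with n = 27 per arm, d = effect/SD, noncentrality d × √(n/2), 52 degrees of freedom, critical value 2.007.

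- HbA1c: d = 0.7/0.9 = 0.778; 0.778 × √13.5 = 2.858; power 80.1%. The smallest total reaching 80% is 54, an exact match.
- Glucose: d = 19/25 = 0.760; 0.760 × √13.5 = 2.792; power 78.2%. The smallest total is 58.
- At 56 completers: 81.5% and 79.8%.

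So 54 is a single-endpoint calculation for HbA1c at the full 0.05. It contains no allowance for multiplicity or joint power.

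**2. What each success rule would imply at 54 completers.** At r = 0 the figures can be checked by hand: family-wise error 1 − 0.95² = 9.75%; false benefit 1 − 0.975² = 4.9%; joint power 0.801 × 0.782 = 63%. The table is from 2,000,000 simulated trials per correlation with pooled t-tests.

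| r (assumed) | Either wins: two-sided family-wise error | Either wins: false claim of benefit (2.5% for one endpoint) | Both required: joint power |
|---|---|---|---|
| 0 | 9.8% | 4.9% | 63% |
| 0.5 | 9.1% | 4.6% | 67% |
| 0.8 | 7.8% | 3.9% | 72% |
| 0.9 | 7.1% | 3.5% | 74% |

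At 56 completers joint power is 65% to 76%. It can never exceed the power of the weaker endpoint.

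**3. What baseline adjustment might recover under a both-required rule.** With baseline-to-week-12 correlation ρ, the effective SD is multiplied by √(1 − ρ²) if the stated SDs are of values, or by √((1 + ρ)/2) if they are of change. Ranges run over r = 0 to 0.9, at 54 completers.

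- SDs of values: 69% to 78% at ρ = 0.3; 80% to 86% at 0.5; 87% to 91% at 0.6.
- SDs of change: 80% to 86% at ρ = 0.5; 73% to 81% at 0.7; 66% to 76% at 0.9.

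The documents give neither ρ nor the type of SD.

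**4. When the interim falls.** Enrolment of 60 at 15 per month ends at 60/15 = month 4.0. The 28th participant enters at 28/15 = month 1.87 and completes 12 weeks (2.76 months) later, at about month 4.6 with no dropout. Enrolment is still open at that point only if 60/a > 28/a + 2.76, that is, if the monthly rate a is below 32/2.76 = 11.6.

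**The case against.** The strongest reply concerns the interim. A reader might infer that an arbitrary choice of endpoint could cut the trial short. The plan's own accrual figures do not support that: all 60 would be enrolled before the 28th completer, a stop is described as a stop to enrolment, and participants already in the study continue to week 12. How often the two endpoints would disagree at the boundary cannot be stated either, because the SEQDESIGN boundary values are not shown. This objection stands. What remains is which endpoint can be declared at the interim, and truncation if accrual runs below about 12 per month.

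Second, a reader might infer that the trial is underpowered at 63% to 74%. Those figures belong to an unadjusted t-test under a both-required rule. The plan specifies a mixed model that includes baseline and, for glucose and HbA1c, a week-6 value that step 3 does not credit. No shortfall under the planned analysis is shown, so this stands too. Equally, the documents do not show that 80% is reached.

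Third, a reader might infer that the plan permits a win on either endpoint. It does not say so; it is silent, and the error inflation is conditional on that rule. Glucose and HbA1c both measure glycaemia, so zero correlation is an extreme bound. Even at 0.9, though, the either-endpoint error is about 7%.

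Finally, this is a small single-site trial whose authors expect confirmatory work, and the remedy is a few sentences. That shows the repair is cheap; it does not supply the missing rule. The HbA1c trigger under Biochemical analyses does not fill the gap, since it governs only whether AGEs are assayed.

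**Conclusion.** The point holds. Two primaries share one alpha and one power statement, and the success rule is missing. Testing each at 0.05 and claiming on either would give about 7% to 10% two-sided error across the pair, and about 3.5% to 5% false claims of benefit. Requiring both would hold alpha and give about 63% to 74% power on the t-test basis, possibly 80% or more under the mixed model. These ranges rest on assumed endpoint correlations of 0.9 to 0, two-sided tests and no allowance for the interim look. The sample size itself is not wrong: 54 is right for HbA1c alone, and the 78.2% for glucose is a rounding matter.

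The unnamed interim endpoint is a genuine gap, but its main effect at planned accrual is on what may be declared early. The AGE mismatch is a minor inconsistency of wording.

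**What to change.** Before the interim analysis is unblinded:

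1. State one success rule. The simplest that keeps the basis for 54 is week-12 HbA1c first at two-sided 0.05, with fasting glucose tested only if HbA1c is significant.
2. Name HbA1c as the endpoint for the SEQTEST boundary, and state the boundary that would apply to glucose if HbA1c crosses at the interim.
3. Restate power per endpoint at 54 completers: about 80% for HbA1c and 78% for glucose, each alone in a fixed-sample test. Confirm both under the SEQDESIGN boundaries actually used.
4. Bring the synopsis objective on AGEs into line with their secondary status under Study endpoints.

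**Cost.** Wording and one power restatement; no added patients or data. The real price is that glucose cannot win on its own, and its chance of being declared becomes the joint figure (63% to 74% on the t-test basis, higher if baseline adjustment helps).

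Two other rules are acceptable if their power is restated. One is to require both endpoints, giving the analysis, SD type and correlations assumed. The other is to test each at 0.025, which at 54 completers gives 70.8% for HbA1c and 68.6% for glucose by t-test.

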## **Adverse Event Definitions**

Adverse Event (AE): An AE is any undesirable medical event occurring to a subject in a clinical trial, if related to the trial product(s). This includes events reported from the first trial related activity after the subject has signed the informed consent and until post treatment follow-up period as defined in the protocol. The following should not be recorded as AEs, if recorded as medical history/concomitant illness on the CRF at screening:

- Pre-planned procedure, unless the condition for which the procedure was planned has worsened from the first trial related activity after the subject has signed the informed consent
- Pre-existing conditions found because of screening procedures

Clinical Laboratory Adverse Event: A clinical laboratory AE is any clinical laboratory abnormality regarded as clinically significant i.e. an abnormality that suggests a disease and/or organ toxicity and is of a severity, which requires active management, (i.e. change of dose, discontinuation of trial product, more frequent follow-up or diagnostic investigation).

Serious Adverse Event (SAE): A serious AE is an experience that at any dose results in any of the following:

- Death
- A life-threatening\* experience
- In-patient hospitalization or prolongation of existing hospitalization
- A persistent or significant disability/incapacity
- A congenital anomaly/birth defect
- Important medical events that may not result in death, be life-threatening\*, or required hospitalization may be considered an SAE when, based upon appropriate medical judgement, they may jeopardize the subject and may require medical or surgical intervention to prevent one of the outcomes listed in this definition.

Unanticipated (Unexpected) Adverse events: The terms “unanticipated” and “unexpected” refer to an event or problem in VA research that is new or greater than previously known in terms of nature, severity, or frequency, given the procedures described in protocol-related documents and the characteristics of the study population.

Serious unanticipated problems involving risks to subjects or others include:

- (1) Interruptions of subject enrollments or other research activities due to concerns about the safety, rights, or welfare of human research subjects, research staff, or others.
- (2) Any work-related injury to personnel involved in human research, or any research-related injury to any other person, that requires more than minor medical intervention (i.e., basic first aid), requires extended surveillance of the affected individual(s), or leads to serious complications or death.

Serious Adverse Drug Reaction (SADR): An adverse drug reaction (ADR) is an adverse event for which a causal relationship (Possible/Probable relation) between the study drug and the occurrence of the event is suspected. The ADR should be classified as serious if it meets one or more of the seriousness criteria.

Non-Serious Adverse Event: A non-serious AE is any AE which does not fulfil the definition of an SAE.

Severity Assessment Definitions:

- Mild: Transient symptoms, no interference with the subject’s daily activities
- Moderate: Marked symptoms, moderate interference with the subject’s daily activities
- Severe: Considerable interference with the subject’s daily activities, unacceptable

Related AE or a Related Problem: A “related” AE or a “related” problem in VA research is an AE or problem that may reasonably be regarded as caused by, or probably caused by, the research.

Collection, Recording and Reporting of Adverse Events: All events meeting the definition of an adverse event must be collected and reported from the first trial related activity after the subject has signed the informed consent and until the end of the post-treatment follow-up period as stated in the protocol.

Follow-up of Adverse Events: During and following a subject’s participation in a clinical trial, the sponsor-investigator and institution will provide adequate medical care to the study subject for

any study-related adverse events, including clinically significant laboratory values related to the study as per local VA policy.

All adverse events classified as serious or severe or possibly/probably related to the trial product must be followed until the subject has recovered, is recovering, or the condition has reached a new stable condition, and all queries have been resolved according to local VA policy.

Pregnancy: Study subjects will be instructed to notify the sponsor-investigator immediately if they become pregnant. Pregnancy complications should be recorded as adverse event(s). If the infant has a congenital anomaly/birth defect this must be reported and followed up as a serious adverse event.

Overdose: An overdose is defined as the accidental or intentional administration of any dose of a product that is considered both excessive and medically important. All occurrences of overdose must be reported as an SAE.

Timeline: We anticipate completion of study about 8 months after recruiting the first patient.

Implications and Future Directions: If successful, this study may provide support for adding Lysulin or comparable supplements as add-on treatment in T2D. However, definitive confirmation of these findings and a more thorough exploration of the relevant signaling events will be needed and could be effectively pursued using animal and cell models. Future long-lasting RCT will be needed to establish whether these types of supplements provide long-term improvement of glycemic control and reduce the risk of diabetes complications.

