Ethical considerations: The study is testing a potential benefit of a diabetes supplement and is not providing a direct clinical benefit to the research subject. Participation in the study will be voluntary and won't affect standard of care. The VA has very strict research guidelines regarding clinical research. All protocols receive IRB, safety, scientific and privacy committee reviews and approval before being initiated. Audits of all studies are conducted by the compliance officer on annual basis: these include consent audits; case report form audits and other study conduct activity. All studies and their adverse events are also reviewed annually by the IRB. The study will be conducted in accordance with the Declaration of Helsinki, all local and national VA policies, and adhere to ICH GCP guidelines.

Payment Schedule: Study participants will be reimbursed \$15 for screening visit and \$25 for each completed study visit for up to \$115 for the whole study.

Reporting of Adverse Events: There is a VA policy for reporting serious adverse events, unexpected/unanticipated adverse events, and standard adverse events. Depending on the category of the event, it is reported within 5 days or annually to the IRB.

The sponsor-investigator will be responsible for reporting of all serious adverse events (SAE), unexpected/unanticipated adverse events, and standard adverse events to the appropriate authority and independent ethics committee/institutional review boards based upon federal regulations and local/IRB policies.

If the SAE or problem is UNANTICIPATED (i.e., it reflects a RISK that is NEW or GREATER than previously known) then this would be reported more rapidly and within the required local expedited

policy time frame but if the AE or problem was ANTICIPATED, this would be reported in accordance to the local policy (e.g., which may be an AE reported at continuing review).

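### The adverse event definition requires relatedness to the product, so non-serious, non-laboratory clinical events judged unrelated need not be collected as AEs

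*Combined protocol and SAP*

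**What the plan says.** The general definition, at the start of Adverse Event Definitions, reads "An AE is any undesirable medical event occurring to a subject in a clinical trial, if related to the trial product(s". The next sentence sets the window: from the first trial activity after consent to the end of post-treatment follow-up.

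Three later rules in that section build on the definition:

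- Collection: "All events meeting the definition of an adverse event must be collected and reported".
- Non-serious events: "A non-serious AE is any AE which does not fulfil the definition of an SAE".
- Follow-up: "All adverse events classified as serious or severe or possibly/probably related to the trial product must be followed", until recovery or a stable state.

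Other classes are worded without a relatedness test. For laboratory findings, "A clinical laboratory AE is any clinical laboratory abnormality regarded as clinically significant". For pregnancy, "Pregnancy complications should be recorded as adverse event(s". Every overdose is to be reported as a serious event. The serious event definition is by outcome: "A serious AE is an experience that at any dose results in any of the following". Under Reporting of Adverse Events in STUDY APPROACH, the sponsor-investigator "will be responsible for reporting of all serious adverse events (SAE"), together with unexpected or unanticipated events and standard adverse events.

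**The concern.** Causality is normally an attribute recorded about an event. Here it is a condition for the event being an AE at all. A blinded, randomised comparison can reveal harms that nobody suspected, because the arms can be compared without relying on anyone's opinion about individual cases. That advantage is lost for any event type screened out by opinion before it is recorded.

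The setting makes attribution to something else easy. The background section expects little toxicity because the ingredients are natural, and participants may be taking oral antihyperglycaemic agents and insulin, so another explanation will often be at hand. At stake is the completeness of the safety record by arm. Nothing here bears on glucose, HbA1c or the other efficacy endpoints.

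**Working it through.** No arithmetic applies. The plan states no figure on this point and gives no event rates. The check is to set the provisions side by side.

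**Step 1: what the collection duty covers.** The general definition makes an event an AE only if it is related to the product. The collection rule reaches only events meeting the definition. The non-serious class consists of AEs that are not serious, so it inherits the condition. A non-serious clinical event judged unrelated, and not a laboratory finding, pregnancy complication or overdose, is therefore outside the duty.

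**Step 2: the time window.** AEs count from the first trial activity after consent. Under Study Visits Schedule, consent and screening come first, then baseline testing (the same day or a separate day) and randomisation, and product is dispensed for use after that. An event between consent and the first dose cannot be related to a product not yet taken. For that period the general definition admits nothing, although its own window includes it.

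**Step 3: the exclusions.** The same paragraph excludes pre-planned procedures and pre-existing conditions found at screening. Those exclusions would hardly be needed if only product-related events could qualify.

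**Step 4: the causality subclasses.** An adverse drug reaction is defined as an AE for which a causal relation, possible or probable, is suspected. For general AEs already required to be related, this subset adds nothing. A related AE is separately defined as one caused, or probably caused, by the research. Both definitions presuppose AEs without that attribute.

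**Step 5: the follow-up rule.** It lists serious, severe and possibly or probably related as alternatives, treating relatedness as one attribute among others. This agrees with steps 2 to 4 but is weaker evidence, for the reason given under the objection.

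**Step 6: serious events.** The outcome-based wording points to inclusion regardless of cause. However, the definition describes a serious AE, and AE carries the relatedness condition. The text does not say whether unrelated serious events are covered.

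**The case against.** The strongest reply is that this is a drafting slip with little practical effect. Steps 2 to 4 themselves suggest that the authors had AEs in the usual, cause-free sense in mind. Several provisions would catch events that the definition omits:

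- Side effects and concurrent medical history are entered in the database at each visit, and general health issues are monitored under Diabetes care during the study.
- Unanticipated events are defined by being new or greater in nature, severity or frequency, with no product-relatedness test, and must be reported.
- The protocol commits to ICH GCP and to VA policies.

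Much of this stands, and it lowers the likely consequence. It does not correct the definition. The collection, reporting and follow-up duties attach to AEs, not to medical history entries. The unanticipated class is itself headed as adverse events, so its reach is arguable, and an excess frequency is hard to recognise if the events are not collected. The external policies are not in the documents, so their content cannot be assumed.

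A reader might also infer that the follow-up rule flatly contradicts the definition, because a severe, unrelated, non-serious event would have to be followed without being an AE. The text does not support that. The rule's subject is adverse events, so an event outside the definition is outside the rule. Nor are the terms serious and severe idle in that rule: an unrelated overdose, or a severe unrelated laboratory AE, is followed through them.

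**Conclusion.** The point holds as an internal inconsistency with a limited safety consequence, and it should be corrected. The wording is explicit. As written, the plan does not require non-serious, non-laboratory clinical events judged unrelated to be collected as AEs, and the AE window and the causality subclasses do not fit that definition.

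The consequence is less certain than the wording. It assumes that staff apply the definition literally, which the documents do not show. Three further inferences should be resisted:

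- That unrelated events go unrecorded altogether. Some may enter the database as concurrent medical history.
- That unrelated serious events are excluded. Their coverage is unstated, not denied.
- That the loss can be put as a number or as lost power. There are no event rates, nothing shows how informative the causality opinions would be, and the Statistical Analysis Plan paragraph sets out no comparison of AEs by arm.

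**What to change.** In the general AE definition, replace the closing relatedness condition with *whether or not considered related to the trial product(s)*. Add one sentence stating that this applies to serious adverse events too. Record relatedness as a separate attribute of each event, judged under blinding, if the case report form (which is not in the documents) does not already do so. The collection, non-serious, adverse drug reaction and follow-up wording then fits without further change.

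The cost is one phrase, one sentence, possibly one form field, and some additional entries. Side effects and concurrent medical history are already obtained at each visit, so no new visit or procedure is needed. A summary of AEs by arm in the Statistical Analysis Plan paragraph would be a sensible but separate addition.
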